### **Additional Analyses**

Additional analyses will be conducted with repeated measures ANOVA using all time points--baseline, 3, 6, and 12 months assessments of 6MWT distance--to explore the effect of the interaction between treatment and time (treatment\*time), as well as the between-subject group treatment effect (intervention versus control) and the within-subject effect (repeated over time) on 6MWT distance. We will use a mixed model (PROC MIXED in SAS) to perform the repeated measures ANOVA. We will examine both compound symmetry and AR(1) correlation structures. Models will have 6MWT distance at each time point as the dependent variable, and treatment,

time, and treatment-time as independent variables. Models will also have study site and any unbalanced baseline subject characteristics as covariates. Similarly, additional analyses will be conducted with repeated measures ANOVA using all time points--baseline, 3, 6, 9, and 12 months assessments of the secondary outcomes--to explore the effect of the interaction between treatment and time (treatment-time), as well as the between-subject group treatment effect (intervention versus control) and the within-subject effect (repeated over time) on SGRQ-TS, dyspnea score, CRP and IL-6 levels, and daily step count. We will use a mixed model (PROC MIXED in SAS) to perform the repeated measures ANOVA. Models will have the secondary outcome at each time point as the dependent variable, and treatment, time, and treatment-time as independent variables. Models will also have study site and any unbalanced baseline subject characteristics as covariates.

As outlined in our Conceptual Model, we will also explore whether increases in PA (6MWT distance and daily step counts) result in decreases in levels of systemic inflammation and risk of AEs, regardless of treatment arm. Models, adjusting for baseline 6MWT distance or step counts, will examine whether increases in PA independently predict decreases in inflammatory biomarkers and decreased risk of AEs and COPD-related hospitalizations. We will use linear regression models with change in 6MWT distance as the independent variable, and change in IL-6 and CRP as dependent variables. A multivariate regression analysis (PROC GENMOD) will be conducted with number of AEs (or COPD-related hospitalizations) as the dependent variable, and change in daily step count and baseline daily step count as independent variables. Models will account for potential confounders such as study site, season of enrollment, age, gender, comorbid medical conditions, FEV1 % predicted, BMI, and history of prior AEs. We believe we will show that increases in 6MWT and daily step count, regardless of treatment arm, independently predict decreases in CRP and IL-6, and decreases in the risk of AEs and COPD-related hospitalizations. These exploratory models have the potential to provide significant insight into the mechanisms of the beneficial impact of walking and PA on systemic inflammation and COPD-related morbidity. The results of these exploratory analyses will provide estimates for sample size calculations for future research proposals.

(d) Discuss potential problems and limitations of the proposed methods and/or procedures and possible alternative procedures to achieve the specific aims.

Like most clinical trials, the study may face recruitment challenges. We believe that we have carefully examined the number of Veterans with COPD and Internet access and we have an accurate assessment of the number of potential participants eligible for the trial. We acknowledge that there is no attention control group. However, the study is designed to compare the WEB intervention to usual care. Providing attention and social support are critical components of the exercise intervention under study so it would be inappropriate to control for them. An alternative control group could be pulmonary rehabilitation (PR). However, an equivalence trial comparing a program like WEB to PR is a different question than the one we are proposing which is to study the efficacy of WEB. We believe that PR would have greater positive effects on 6MWT distance than WEB. In fact, participation in a PR program within the previous 3 months is an exclusion criterion for the proposed study. Although referral to PR is recommended for the treatment of COPD, the reality is that PR is available for only a small fraction of patients with COPD. We choose counseling, reinforced with written instructions, as the control group to most pragmatically mirror usual care.

We acknowledge that the pedometer captures ambulation, but does not record upper extremity exercise or total PA. However, total walking step count has been shown to be closely related to overall daily activity in persons with COPD, and lower extremity exercise is the most effective and best-validated portion of PR programs (24,27,42,43). Furthermore, the pedometer does not provide information about the intensity of the walking performed. However, the literature and our preliminary data suggest that all forms of walking are beneficial in COPD, whether walking as part of functional community mobility or walking as part of sustained cardiovascular exercise. There may also be selection bias of subjects who are less sick and interested in an exercise research study. In sum, the proposed study has the potential to transform current clinical management of COPD and advance our understanding of how to promote PA in persons with COPD.

(e) If humans or animals are to be studied, power analysis needs to be used to justify the number to be studied. Justify the species of animal to be used. If cell lines or tissue specimens are used, discuss the source of the material.

Please also see Power Calculations above. If the participant provides consent, at each of the four in-person study visits, we will take three tubes of blood (approximately 2 tablespoons) by venipuncture to be stored for investigating blood markers. Blood samples will be used to examine the occurrence of various blood protein markers (i.e. biochemicals that indicate inflammation or other related changes) that may influence overall health. Blood samples will be processed and stored at VA Boston's MAVERIC. Samples will be sent to Boston Children's Hospital for analysis of C-reactive protein and Interleukin-6. To protect confidentiality, blood samples will be stored at VA Boston MAVERIC using only a study code with no personal identifiers.

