Despite the potential benefits, there have been few interventions to increase walking in persons with COPD. Counseling by healthcare providers to increase physical activity and exercise has shown limited success. Although supervised pulmonary rehabilitation programs improve exercise capacity, they are not accessible to all who could benefit from them and have low adherence rates. Novel interventions that incorporate strategies for behavioral change and that are accessible, individualized, and sustained are needed to promote physical activity and exercise in persons limited by COPD. Funded by a RR&D CDA-2 ([name]), we have developed and piloted a novel exercise intervention that combines a website with a pedometer to promote walking in persons with COPD. The program, called Every Step Counts (ESC) for Lung Health, accurately monitors walking, provides iterative feedback and individualized goal-setting in steps per day, and delivers education and motivation online. In a non-randomized study, we demonstrated its safety, feasibility, and ability to increase daily step count in persons with COPD over 3 months.

Building on the CDA-1 and CDA-2, we propose to determine the efficacy of an internet-mediated walking program compared to usual care (verbal and written instructions to exercise). We propose a 2-arm randomized, controlled study (1:1 ratio) in up to 185 persons with COPD.

Subjects will participate in the study for a total of up to 13 months. The intensive interventional phase will be 6 months during which subjects will be engaged by the website with messages, tips, an online forum community, and step count goals followed by a maintenance intervention phase of 6 months during which the subjects will receive new step count goals but no new educational materials; although subjects will be able to review content previously posted. Subjects will wear the pedometer for 14 days preceding or following the 12-month in-clinic visit. For the step collection at month 12, subjects assigned to the control arm will receive a pedometer by postage mail or in person to wear for 14 days and return by prepaid mailer or in person at the 12-month in-clinic study visit. Subjects in the intervention arm will continue wearing their pedometer. Additionally, postcards will be sent during the subject's birthday month (no specific day listed) as well as a postcard during each season (spring, summer, fall, winter) with health and safety tips to enhance study engagement.

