In a previous study, the use of SUH for 4 months resulted in an average increase in walking of approximately 2,000 steps per day (1.6 km) in individuals with type 2 diabetes mellitus, coronary artery disease, or obesity (64). In that study, a subset of persons with self-reported COPD (n=24) demonstrated an average increase of approximately 1,000 steps per day after use of SUH for 4 months (65). Another study has used the core features of SUH to promote PA in women with gestational diabetes (66), while another study is assessing the efficacy of SUH to reduce back pain in Veterans (67). Although it is well known that greater PA and exercise are beneficial, it is unclear how to increase PA in persons with chronic disease such as COPD who already experience significant functional impairment from their disease. As part of her CDA-2, [name] has modified SUH to include website content specific for persons with COPD. This adapted walking program is called Every Step Counts (ESC) for Lung Health. In a non-randomized pilot study, we have demonstrated its safety, feasibility, and ability to increase daily step counts over 3 months in persons with COPD (68).

(b) Significance.

Our proposal addresses the exciting and important next steps of developing novel interventions to promote PA and assessing their impact on COPD outcomes. WEB is unique because of its

ability to accurately monitor walking performed, individualized goal setting, educational content and motivational messages, and automation. We propose to establish the efficacy of WEB to improve short- and long-term outcomes in COPD in a randomized, controlled study. The results of the proposed study will provide the evidence needed to support the adoption of WEB into clinical practice.

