**Power Calculation:** This study is powered on our pre-specified primary outcome of 6MWT distance. Our main comparison is 6MWT distance at 6 months between the WEB intervention and control arms. Our power analysis is based on a widely accepted minimum clinically meaningful change in 6MWT distance of 54 meters and the published standard deviation for 6MWT distance of 80-120 meters (90). Our data in a similar Veteran population showed a standard deviation of 102 meters for 6MWT distance. We use a standard deviation of 100 meters in our power calculation. Using the sample size formula for the comparison of the means of 2 independent samples, we calculate that 55 evaluable subjects in each arm at 6 months will allow

[figure not shown]

detection of a difference of at least 54 meters between the WEB and usual care arms with a power of 80% and  $\alpha=0.05$ . We anticipate a maximal drop-out of 40% at 6 months. In order to have 111 evaluable subjects at 6 months, we plan to enroll a total of 185 subjects.

**Secondary Aims:** To estimate the effect of the WEB intervention on (a) HRQL, as measured by the St. George's Respiratory Questionnaire (SGRQ), (b) dyspnea, (c) CRP and IL-6, (d) risk of AEs and COPD-related hospitalizations, (e) engagement in PA as measured by daily step count, (f) body composition and bone mineral density, and (g) pain.

Our statistical analysis plan for the secondary outcomes is similar to that for the primary outcome. We will use 2-way factor analysis or analysis of variance (ANOVA) to assess the effect of intervention versus control on SGRQ-TS, dyspnea score, CRP and IL-6, and daily step count. We will analyze absolute values of the secondary outcomes at baseline and 6 months. Two-way ANOVA will allow us to examine the effect of our intervention, and additionally allow us to assess the interaction between treatment and time (treatment-time) on the secondary outcomes. We will use a mixed model (PROC MIXED in SAS) to perform the 2-way ANOVA. Models will have SGRQ-TS, dyspnea score, CRP and IL-6, or daily step count as the dependent variable, and treatment, time, and treatment-time as independent variables. Models will also include study site and any unbalanced baseline characteristics as covariates.

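### For 6MWT and the continuous secondary outcomes, none of the effects named in the repeated-measures models isolates month 12, so the plan has no pre-specified estimate of whether a WEB benefit lasts through the maintenance phase

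*Combined protocol and SAP*

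**What the plan says.** The opening rationale describes a six-month intensive phase "followed by a maintenance intervention phase of 6 months during which the subjects will receive new step count goals" without new educational content. The Significance section adds: "We propose to establish the efficacy of WEB to improve short- and long-term outcomes in COPD". The visit schedule (Table 5) repeats the 6MWT, SGRQ, both dyspnea scales, the blood draw and the step count at month 12.

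Under Statistics (power analysis), the primary model takes 6MWT at baseline and month 6. For SGRQ total score, dyspnea, CRP, IL-6 and step count the same section says: "We will analyze absolute values of the secondary outcomes at baseline and 6 months". The anticipated secondary results are also framed at 6 months.

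For these outcomes month 12 appears only under Additional Analyses. The 6MWT model uses baseline and months 3, 6 and 12, "to explore the effect of the interaction between treatment and time (treatment\*time), as well as the between-subject group treatment effect" and the within-subject effect of time. Compound symmetry and AR(1) are both to be examined. A parallel model for the secondary outcomes adds month 9 and names the same three effects. The plan names no month-12 difference between arms and no comparison of month 12 with month 6.

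Two other uses of 12-month data stand apart from this. Exacerbations and COPD hospitalizations are summed over 12 months and compared by negative binomial regression. DXA is done at baseline and month 12 at the Boston site.

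**The concern.** Half of the intervention period is a maintenance phase. A natural question at its end is whether the arms are still apart at month 12 and whether the gap has changed since month 6. An overall treatment-by-time test answers neither. Its null hypothesis is that the between-arm difference is the same at every visit, including baseline. It is false if the arms separate and stay apart, and equally false if they separate and come back together. The averaged treatment effect is non-zero in both cases.

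Two things are at stake. A significant interaction could be mistaken for evidence of a sustained effect. And with no month-12 estimate named, the summary of durability would be chosen after the data are seen.

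**Working it through.** **Inputs from the plan.** The design difference is 54 m, from "detection of a difference of at least 54 meters between the WEB and usual care arms with a power of 80" percent. The SD comes from "We use a standard deviation of 100 meters in our power calculation", and the number from "55 evaluable subjects in each arm at 6 months". Alpha is 0.05. The 6MWT model has four time points, so treatment-by-time has 3 df.

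**Assumptions not in the plan.** Alpha is two-sided. Within-subject correlation ρ is 0.5 to 0.9. The difference at month 3 is x m, from 0 to 54. There are 55 per arm at every visit: the drop-out figure is given for month 6 only, although the exacerbation power statement takes 111 subjects through 12 months. AR(1) is applied by visit order.

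**The plan's own figure.** n per arm = 2(1.960 + 0.842)² × 100²/54² = 53.8, so 54. At 55 per arm, t-test power is 0.801. 111/(1 − 0.40) = 185. The stated sample size reproduces.

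**Interaction test.** Arm differences at months 0, 3, 6, 12 are (0, x, 54, 54) if kept and (0, x, 54, 0) if lost. The noncentrality is λ = (Cd)′[C R C′ · SD² · 2/n]⁻¹(Cd), where d holds these arm differences, C takes each visit minus baseline and R is the correlation matrix. Power is from the noncentral F with 3 and 108 df.

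Under compound symmetry this reduces to λ = n Σ(d − d̄)² / [2 SD²(1 − ρ)]. With x = 27:
- kept: d̄ = 33.75, and Σ(d − d̄)² = 1139.06 + 45.56 + 410.06 + 410.06 = 2004.75
- lost: d̄ = 20.25, and Σ(d − d̄)² = 410.06 + 45.56 + 1139.06 + 410.06 = 2004.75

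At ρ = 0.7, λ = 55 × 2004.75/6000 = 18.38 in both cases. In general, the lost sum minus the kept sum is 27(x − 27). Under compound symmetry the lost case is therefore at least as likely to be significant whenever x is 27 m or more.

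| Structure, ρ | x = 27: kept / lost | x = 54: kept / lost |
|---|---|---|
| CS 0.5 | 0.789 / 0.789 | 0.826 / 0.925 |
| CS 0.7 | 0.956 / 0.956 | 0.971 / 0.995 |
| CS 0.9 | 1.000 / 1.000 | 1.000 / 1.000 |
| AR(1) 0.5 | 0.495 / 0.761 | 0.689 / 0.890 |
| AR(1) 0.7 | 0.647 / 0.951 | 0.882 / 0.989 |
| AR(1) 0.9 | 0.978 / 1.000 | 1.000 / 1.000 |

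Below half the effect at month 3, the order reverses under compound symmetry: with x = 0 and ρ = 0.5, kept is 0.925 and lost 0.826. Under AR(1) the lost case is not less likely to be significant at any x examined.

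**Secondary outcomes.** There are five time points (4 df), with 0.55 SD at month 6, half of that at month 3, and 108 denominator df. At ρ = 0.5 under compound symmetry, kept gives 0.828, loss complete by month 9 gives 0.828, and gradual loss by month 12 gives 0.769. Under AR(1) the figures are 0.489, 0.736 and 0.591.

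**Averaged effect.** Over the four visits with x = 27 the mean difference is 135/4 = 33.75 m if kept and 81/4 = 20.25 m if lost. For x from 27 to 54 and ρ from 0.5 to 0.9, power is 0.45 to 0.84 if kept and 0.20 to 0.50 if lost.

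**Direct contrasts.** For the month-6-to-12 change in the between-arm difference, SE = √[4 SD²(1 − ρ)/55] under either structure: 19.1, 14.8 and 8.5 m at ρ = 0.5, 0.7 and 0.9. Power to detect full loss of 54 m is 0.81, 0.96 and 1.00, with a 0.05 rejection rate if the benefit is kept. For the difference in change from baseline to month 12, power if 54 m is kept is 0.81 (CS 0.5), 0.96 (CS 0.7), 0.57 (AR(1) 0.5) and 0.70 (AR(1) 0.7), with a 0.05 rejection rate if it is lost.

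**The case against.** The strongest reply is that the plan never makes durability a hypothesis. The hypothesis on 6MWT is at 6 months, the largest difference is predicted there, and the repeated-measures models are labelled exploratory. The fitted model, with time as a factor, can produce arm differences at every visit. All of this stands. It makes the gap one of pre-specification rather than of data or model, and it limits the point to a should-fix.

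Several stronger readings are tempting, and the documents do not support them.
- A reader might infer that the trial uses month-12 data nowhere else. The 12-month event counts and the month-12 DXA show otherwise. They do not fill this gap: the counts pool both phases, and DXA has no month-6 measurement.
- A reader might infer that the trial fails a stated aim. The wording on long-term outcomes is general and sets no month-12 endpoint.
- A reader might infer that the interaction test is equally likely to be significant in both cases. That is exact only under compound symmetry with half the effect at month 3. Under AR(1) the lost case is usually clearly more likely.
- A reader might infer that the averaged effect is blind to loss. It responds to loss, but it includes baseline and mixes visits.
- A reader might infer that the investigators intend to claim durability from a significant interaction. Nothing in the text says so.

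**Conclusion.** The point holds for 6MWT, SGRQ, dyspnea, CRP/IL-6 and step count. The named effects cannot show whether a benefit lasted. For 6MWT, if at least half the 54 m is present at month 3, a significant interaction is no more likely when the benefit is kept than when it is fully lost, and under AR(1) at ρ = 0.7 it is much less likely (0.65 against 0.95). The secondary-outcome models behave similarly, except that gradual loss under compound symmetry gives a rejection rate about 6 points lower at ρ = 0.5.

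The sizes rest on the assumed correlations, the assumed month-3 effect, two-sided alpha and no loss after month 6. The qualitative conclusion does not: neither the interaction nor the averaged effect is a month-12 contrast. The month-6 primary conclusion is untouched.

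**What to change.** Under Additional Analyses, state that time enters PROC MIXED as a factor. For 6MWT and each continuous secondary outcome measured at month 12, pre-specify with 95% CIs:
1. the between-arm difference in change from baseline to month 12;
2. the change in the between-arm difference from month 6 to month 12.

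Base any statement on durability on these two estimates and report the interaction test descriptively. Read contrast 2 from its interval, not from a non-significant p-value. At ρ = 0.7 the half-width is 1.96 × 14.8 = 29 m, so full loss of 54 m can be told from none, but smaller losses may not be.

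Compute both contrasts on observed month-12 data under the mixed model. The section on minimizing attrition and handling missing data fills visits missed for reasons other than worsening COPD with the last observed value. A subject carried forward from month 6 then has a month-6-to-12 change of exactly zero, which biases contrast 2 toward a benefit that appears kept.

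The cost is two ESTIMATE statements per outcome and a few sentences in the analysis plan. No new data are needed.

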Based on our previous work, medical problems and temporary suspension from the exercise program will be the most common reason for missing outcomes data in both arms. We have designed the testing windows to minimize missing data. At months 3 and 6, testing will be allowed within a window of  $\pm 2$  weeks. At months 9 and 12, testing will be allowed within a window of  $\pm 1$  month, making the total participation time up to 13 months from the baseline in-clinic study visit (C00). Despite our efforts at follow-up, some missing data are expected with multiple testing visits. We will collect the reasons for missing data such as death, COPD exacerbation, medical reasons, or non-medical reasons. We will compare the rate of losses to follow-up at 3, 6, 9, and 12 months among the two arms using the chi-square test of association. We will assess whether any baseline characteristics such as age, FEV1 % predicted, or 6MWT distance, are associated with losses to follow-up using chi-square tests for categorical baseline data and analysis of variance for continuous baseline data. If baseline variables and treatment group are found to be associated with loss to follow-up, then the analysis models will be modified to include the differing baseline variables as covariates to provide unbiased estimates of intervention effects. For subjects who discontinue the study early due to worsening of COPD or due to death, missing outcome data will be imputed using the least favorable data observed prior to discontinuation. Missing data for subjects who miss a visit not related to worsening of COPD will be imputed using last observed data. We will also perform sensitivity analyses using the complete case method, excluding those with no observed outcome at 6 months.

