### **Statistics (power analysis)**

Prior to analyzing the outcomes, we will summarize and compare baseline demographic and clinical variables by treatment group. Any unbalanced characteristics occurring despite randomization will be assessed as potential confounders in multivariate analyses. Analyses will be performed with the SAS statistical software package (9.3, SAS Institute; Cary, NC).

**Primary Aim:** To determine the efficacy of the WEB intervention to increase 6MWT distance.

We focus on 6MWT distance at 6 months since we predict that the greatest difference in 6MWT distance between study arms will occur at month 6, at the end of the interventional phase. We have revised our statistical analysis plan to use 2-way factor analysis or analysis of variance (ANOVA). This approach will assess the effect of intervention versus control on 6MWT distance, using absolute measures of 6MWT distance at baseline and 6 months. Two-way ANOVA will allow us to assess the effect of treatment (intervention versus control), and additionally allow us to assess the interaction between treatment and time (treatment-time) on 6MWT distance. We will use a mixed model (PROC MIXED in SAS) to perform the 2-way ANOVA given its flexibility of modeling the variances and covariances, its robustness in accounting for correlated data (repeated measures data), and its flexibility in handling missing data. Models will have 6MWT distance as the dependent variable, and treatment, time, and treatment-time as independent variables. In this approach, models will also include study site and any unbalanced baseline characteristics as covariates. Primary analyses to determine the effect of WEB on 6MWT distance will use the intention-to-treat approach to include as many randomized subjects as possible in the analyses. Subjects will be considered to be in his/her randomly assigned arm no matter how much he/she participated in it. As a sensitivity analysis, however, we will examine 6MWT distance on a per-protocol basis, where noncompliant subjects ( $\geq 30\%$  of days with no exercise performed on logs) in each treatment arm will be excluded from the analysis.

**Anticipated Results:** We anticipate that subjects in the intervention group will have significantly higher 6MWT distance than subjects in the control group at 6 months.

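### In the exploratory 0, 3, 6 and 12-month 6MWT model, AR(1) ignores the longer last gap and compound symmetry assumes no decay, so neither named structure is safe for all change contrasts

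*Combined protocol and SAP*

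**What the plan says.** The section Additional Analyses plans a model of 6MWT distance that uses the "baseline, 3, 6, and 12 months assessments of 6MWT distance". Its purpose is "to explore the effect of the interaction between treatment and time", together with the group effect and the within-subject time effect. On software it says "We will use a mixed model (PROC MIXED in SAS) to perform the repeated measures ANOVA", and on covariance "We will examine both compound symmetry and AR(1) correlation structures". It names no unstructured or time-based matrix, no robust SE, and no rule for choosing between the two structures. Table 5 confirms that no 6MWT is done at month 9, so the gaps are 3, 3 and 6 months.

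Two neighbouring statements limit the scope. The primary analysis in Statistics (power analysis) is a separate model "using absolute measures of 6MWT distance at baseline and 6 months", so it has two time points. For the secondary outcomes, Additional Analyses lists "baseline, 3, 6, 9, and 12 months assessments of the secondary outcomes" and names no covariance structure.

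**The concern.** TYPE=AR(1) indexes visits 1 to 4 and sets the correlation to ρ raised to the difference in visit rank. Months 6 and 12 are therefore treated as being as close together as months 0 and 3. If correlation falls with elapsed time, the model makes the 6-to-12-month pair look more alike than it is, and the SE of that change comes out too small. CS does not use spacing and so does not share this defect, but it gives the 0-to-12-month pair the same correlation as adjacent visits. If correlation decays, the 0-to-12-month SE comes out too small.

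This is the only planned 6MWT model that uses month 12, so change during the maintenance phase would naturally be read from it. With no selection rule, the structure could also be chosen after the results are seen.

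**Working it through.** **Inputs.** Visit times 0, 3, 6 and 12 months (Additional Analyses; Table 5). SD 100 m: "We use a standard deviation of 100 meters in our power calculation". 55 evaluable subjects per arm (Statistics, power analysis). The documents give no within-subject correlation and no figure for this model, so the correlations below are assumptions. SD and n set the scale only; the SE ratios do not depend on them.

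**The plan's own figure.** For 54 m, SD 100 m, 80% power and two-sided α = 0.05, the normal formula gives 2 × (1.960 + 0.842)² × 100² / 54² = 53.8 per arm. The t-test version gives 55, and 111 / 0.60 = 185. The sample size reproduces and does not involve the structures at issue.

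**Method.** Assume complete data, equal variances and a separate mean for each arm and visit. The fitted structure is the one that maximises the expected Gaussian likelihood. Here that gives:

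- AR(1): ρ = mean of the three adjacent-visit correlations
- CS: ρ = mean of all six pairwise correlations
- SE of a between-arm change = 100 × √(2/55) × √(2(1 − corr)), with 100 × √(2/55) = 19.07 m
- Type I error = 2Φ(−1.96 × model SE / true SE)

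**Worked case: exponential decay, 3-month correlation 0.80.** True correlations are 0.80 (0-3 and 3-6), 0.64 (0-6 and 6-12), 0.512 (3-12) and 0.4096 (0-12).

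- AR(1) fits ρ = (0.80 + 0.80 + 0.64)/3 = 0.747.
- CS fits ρ = (0.80 + 0.80 + 0.64 + 0.64 + 0.512 + 0.4096)/6 = 0.634.
- 6-to-12 change: true SE 19.07 × √0.72 = 16.2 m. AR(1) gives 19.07 × √(2 × 0.253) = 13.6 m, ratio 0.84, type I error 0.100. CS gives 16.3 m, ratio 1.01.
- 0-to-6 change: true SE 16.2 m. AR(1) uses 0.747² = 0.558 and gives 17.9 m, ratio 1.11.
- 0-to-12 change: true SE 19.07 × √1.181 = 20.7 m. CS gives 16.3 m, ratio 0.79, type I error 0.123. AR(1) uses 0.747³ = 0.416 and gives 20.6 m, ratio 0.99.

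**Range under exponential decay (model SE / true SE).**

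| Contrast between arms | 0.70 | 0.80 | 0.90 | 0.95 |
|---|---|---|---|---|
| AR(1), 6-to-12 | 0.85 | 0.84 | 0.83 | 0.82 |
| AR(1), 0-to-6 | 1.09 | 1.11 | 1.13 | 1.14 |
| AR(1), 0-to-12 | 0.99 | 0.99 | 1.00 | 1.00 |
| CS, 6-to-12 | 1.00 | 1.01 | 1.02 | 1.03 |
| CS, 0-to-12 | 0.82 | 0.79 | 0.76 | 0.75 |
| Either, month 12 itself | 1.00 | 1.00 | 1.00 | 1.00 |

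Type I error is 0.095 to 0.107 for the first row and 0.110 to 0.143 for CS 0-to-12.

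**Other correlation shapes.**

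- Stable subject effect (60% of variance) plus decay (40%), no noise: the AR(1) 6-to-12 and CS 0-to-12 ratios are the same as in the table.
- Subject effect, decay and measurement noise at 60/30/10%: AR(1) 6-to-12 ratio 0.91 to 0.96, CS 0-to-12 ratio 0.87 to 0.92. The understatement is about 4 to 13%.
- Constant correlation: CS is exact throughout. AR(1) is exact for 6-to-12 but overstates the 0-to-12 SE by about 48 to 69%. At 0.80: √(2(1 − 0.512)) / √(2(1 − 0.80)) = 0.988/0.632 = 1.56.

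**The test the plan names.** Under exponential decay, the 3-df treatment-by-time test has size of about 5.3 to 5.5% with AR(1) and about 6 to 7% with CS.

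**The case against.** The strongest reply is that little of consequence is exposed. The plan calls the analysis exploratory and says that both structures will be examined, which would show sensitivity to the choice. Its named target is the treatment-by-time interaction, whose size is barely disturbed; the 10 to 14% error rates belong to single contrasts that the plan does not list. Each affected later contrast is nearly right under the other structure: CS for 6-to-12, AR(1) for 0-to-12. All of this stands, and it limits the point to a refinement. It does not remove it: under decay no single named structure serves both contrasts, and the plan has no rule for which to report.

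A reader might infer more than the documents support:

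- *That the 12-month result has a wrong SE.* With complete data and equal variances, the between-arm SE at month 12 does not depend on the correlation. Missing data make this approximate. For example, if 80, 60 and 50% remain at months 3, 6 and 12 (assumed, missing at random, no imputation, decay as above), the CS ratio at month 12 is 0.91 to 0.94.
- *That CS is no help at all.* It is exact under constant correlation and nearly right for 6-to-12 under decay.
- *That the SEs are wrong whatever the data look like.* That depends on a correlation pattern the documents do not give. If correlation happened to follow visit order, AR(1) would be exact.
- *That the biomarker models share the flaw.* The covariance sentence belongs to the 6MWT model only.

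**Conclusion.** The point holds as a minor, conditional one. AR(1) is a poor match to visits at 0, 3, 6 and 12 months, and CS does not cover every contrast if correlation decays with time. Under exponential decay at an assumed 0.70 to 0.95 per three months, with complete data, the error is an SE about 15 to 18% too small for the 6-to-12-month change and 9 to 14% too large for 0-to-6 under AR(1), and 18 to 25% too small for 0-to-12 under CS. Measurement noise reduces the two understatements, and constant correlation makes CS correct.

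It would be wrong to read this as a threat to the main result. The primary model has two time points, where AR(1) and CS are the same model, so the primary analysis and the 185-subject sample size are unaffected.

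**What to change.** For this model, pre-specify TYPE=UN with Kenward-Roger degrees of freedom in place of the two named structures. Four visits need 4 × 5 / 2 = 10 covariance parameters, which is feasible with about 111 evaluable subjects, and the matrix imposes no spacing or decay pattern. If it fails to converge, use a simpler named structure with robust (empirical) SEs.

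Spatial power on actual months should not be the fallback by itself. It is right under exponential decay, but if correlation is constant (0.7 to 0.9) it overstates the 6-to-12-month SE by 23 to 27% and the 0-to-12-month SE by 53 to 73%, where CS would be exact.

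Table 5 shows no blood draw at month 9, so CRP and IL-6 also fall at 0, 3, 6 and 12 months. No structure is named for them, and the same unstructured matrix can be stated there.

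The cost is one line of SAP and code and a few more covariance parameters. No visits, data collection or sample size change.
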